#### **F. Treatment modifications**

Patients will be monitored for their ability to tolerate the study medication during weekly follow-up telephone calls. If necessary, anti-diarrheal or anti-emetic therapy may be prescribed to ease any discomfort associated with the medicine. If a patient cannot tolerate the study medication and misses two or more doses in a row, they will be withdrawn from the study.

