## Protocol Summary

This is a randomized, open-label clinical investigation of the effects of short-term oral metformin therapy on biomarkers for tumor growth in subjects with endometrial cancer. Metformin is a well-tolerated drug widely prescribed for treatment of Type 2 diabetes mellitus and for treatment of Polycystic Ovarian Syndrome (PCOS) in non-diabetic women. Clinical trials are ongoing to explore this possibility in breast cancer (NCT01101438). This investigation is the first study of metformin in endometrial cancer patients, and is designed to understand the mechanism of its anti-cancer actions, if any, and its interactions with biomarkers in endometrial cancer patients.

Forty non-diabetic subjects will be randomized so that 20 will receive oral metformin for 14-21 days and the remaining 20 will receive no metformin for 14-21 days. Subjects will be monitored for adverse events (AEs). All subjects will have blood samples collected on Day 1 (prior to start of metformin for subjects randomized to metformin) and prior to surgery. These samples will undergo metabolic, lipid and tumor-specific biomarker analyses. Tumor and adjacent normal tissue taken from subjects from the diagnosis and at the time of surgery will be analyzed for cellular proliferation, apoptosis and biomarker levels.

The **Primary objectives** of this study are as follows:

1. To determine the effect of metformin on tissue markers of proliferation, apoptosis, and insulin-mediated signaling in endometrial cancer in non-diabetic obese women.
2. To determine the tolerability of a short course of metformin in non-diabetic obese women with newly diagnosed endometrial cancer.

The **Secondary objectives** of this study are as follows:

1. To determine the effect of metformin on HbA1c and blood lipid profiles measured at baseline and just before surgery.
2. To determine the effect of metformin on the following hormones measured in blood plasma at baseline and just before surgery: Insulin, IGF-I, leptin, and adiponectin.
3. To determine the effect of metformin on the expression levels of mRNAs and miRs measured in blood plasma at baseline and just before surgery.
4. To determine the effect of metformin on the expression levels of mRNAs and miRs measured in tumor and adjacent non-tumoral uterine tissue.

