#### **A. Method of assigning subjects to treatment groups.**

Subjects will be assigned randomly to one of two groups. Group 1 will receive treatment with metformin, while Group 2 will receive no treatment. Subjects assigned to Group 1 will be administered oral metformin at 500 mg twice a day for 14-21 days followed by surgery. These doses are therapeutic, and will permit patients to undergo their surgical therapy within an appropriate time frame.

Subject eligibility will be established before treatment randomization. Once a subject's eligibility is determined, the Research Staff will be notified to implement the randomization process. Randomization will be completed when the Research Staff receives a copy of the signed consent and the physician's orders for study agent to be dispensed.

To minimize imbalance between treatment arms, the randomization procedure will employ a stratified block randomization with randomly chosen blocks of size 2, 4, and 6, and with BMI as the stratification factor. Randomization will be conducted using sealed envelopes located at the Cancer Clinical Trials Office (CCTO). There will be two sets of consecutively numbered envelopes, one set for subjects with BMI from 30 to 39.9 and one set for subject with BMI of 40 or higher. At each randomization, the lowest numbered envelope will be chosen. The Research Staff will open the envelope and assign the subject to the treatment arm based on the contents of the envelope. The appropriate treatment will then be dispensed to the subject.

Methods for ensuring blinding.

Not applicable: this is an open-label study.

Methods for unblinding the study.

Not applicable: this is an open-label study.

Procedure for unblinding in case of medical emergency.

Not applicable: this is an open-label study.

Metformin will be administered to patients (randomized to receive metformin) for a minimum of 14 days and a maximum of 21 days, representing the typical time interval between confirmation of tumor diagnosis and surgical resection. Following surgical resection, any unused study drug will be returned to the physician at the time of the subject's first post-operative visit.

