**B. Blood Draws and Laboratory Tests**

Blood will be drawn from each subject, approximately 18 mL in purple top vacutainers, prior to treatment assignment (if not preformed previously as conventional care) and after completion of the therapy at the time of surgery. The blood sample below will be subjected to the following tests at the UAMS Clinical Laboratory:

- a) A comprehensive metabolic panel (glucose, calcium, albumin, total protein, sodium, potassium, CO2, chloride, BUN, creatinine, ALP, ALT, AST and total bilirubin), to be performed prior to starting treatment only.
- b) A lipid panel (cholesterol, HDL-C, LDL-C, triglycerides), to be performed both prior to treatment assignment and at the time of surgery.
- c) Determination of HbA1c, to be performed both prior to treatment assignment and at the time of surgery.

The blood samples listed below will be utilized for correlative laboratory studies in the research laboratory of [name] at the UAMS Biomed Bldg. Aliquots of each blood sample will be centrifuged to separate out the plasma portion. Plasma will be stored at -80°C in the Co-Investigator's lab until analysis is performed.

The following biomarkers will be assayed in the plasma samples collected at baseline and at the time of surgery through enzyme-linked immunosorbent assays (ELISA) or multiplex assays. All of these tests will be performed by laboratory personnel in [name] lab:

- a) Insulin
- b) Leptin
- c) Adiponectin
- d) IGF-I and IGF-II

Remaining plasma samples will be subjected to global profiling of miRs and mRNAs to evaluate/validate the relative expression of specific candidate metformin-regulated miRs and mRNAs ([name] lab). miR and mRNA levels will be determined using quantitative SYBR green-based real time reverse transcriptase polymerase chain reaction (RT-PCR) assays and a microarray platform. These tests will be performed in [name] laboratory by his personnel and/or by commercial providers of microarray profiling services.

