### **C. Tissue Specimens and Laboratory Tests**

A sample of tumor with adjacent normal mucosa will be obtained after surgery from the Pathology department from the tissue remaining after normal gross and histological assessments.

Fresh tissue samples will be transported by designated research personnel to [name] laboratory at the UAMS Biomed Bldg. Fixed tumor and 'normal' tissues will be subjected to IHC for markers of proliferation (*Ki-67*, phospho-histone H3), and apoptosis (TUNEL, cleaved caspase-3). Tumor (and 'normal') tissues will also be examined by Western blot and/or ELISA for expression levels of FASN, total and phosphorylated insulin receptors, and total and phosphorylated IGF-I receptors. Total and phosphorylated AMPK levels will be assessed by IHC or Western blot. Lastly, tissues will be used for miR and mRNA profiling.

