#### **G. Subject removal**

Any patient who develops a grade 3 or higher gastrointestinal toxicity while on study will be discontinued. Subjects that withdraw from the study or that are withdrawn from the study due to unacceptable toxicity will return all unused study drug at their next scheduled clinic appointment.

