### **Feasibility of Study Population Recruitment:**

At the UAMS Gynecologic Oncology clinic, approximately 160 new cases of endometrial cancer in obese women are seen each year (three new cases per week). The majority of these women are not diabetic at the time of the diagnosis of endometrial cancer. This represents the target population for this study. All new patients are seen by [name] or [name]. Except in rare circumstances, all these women will be scheduled for hysterectomy and bilateral salpingo-oophorectomy to stage their cancer. The typical time period between initially being seen by [name] or [name] and surgery is approximately 3 weeks. Thus, those women who agree to participate in this trial can begin the intervention with metformin and expect no delay to the time of their surgery.

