### Study Calendar

Procedure	Pre-study	Study Period					Post-Operative clinic visit / Early Termination f
		Day 1 (Day of first dose)	Day 8			Days 14 -21 (Surgery)	
Eligibility Assessments							
Informed Consent	X						
Inclusion/Exclusion Criteria	X						
Medical History	X						
Study Assessments							
Physical Examination	X	X					
Physical Measurements e	X	X			X		
Demographics h	X						
Vital signs b		X					
Body Mass Index (BMI)	X				X		
Smoking Status	X						
Alcohol Status	X						
Concomitant Medications j	X	X	X k		X		
Adverse Events (AEs)		X	X k		X		
Telephone contact			X k				
Laboratory Test							
CBC Panel c	X				X		
Comprehensive Metabolic Panel	X				X		
Lipid Panel (Cholesterol, HDL-C, LDL-C, Triglycerides) *	X				X		
Urine Pregnancy Test d		X					
HbA1c *	X				X		
Study labs (send to [name] lab) g	X				X		
Clinical Drug Supplies							
Randomize		X					
Dispense study drug		X					
Dispense patient diary		X					
Review of drug diary			X k				
Collect unused study drug							X
Collect subject diary							X
Pathology							
Tumor Stage							X
Tumor Differentiation	X						X
Lymph Node Involvement							X
Tissue Collection (send to [name] lab)	X i				X		

\*Above standard of care (investigational-to be paid for by grant).

a A comprehensive panel will determine the following serum levels for the following: glucose, calcium, albumin, total protein, sodium, potassium, CO2, chloride, BUN, creatinine, ALP, ALT, AST, and total bilirubin (standard of care).

b Temperature, blood pressure, pulse, respiration rate.

c WBC, Platelets, Hb

d Within 7 days of randomization

e Physical measurements to include ECOG, performance status, weight and height (height only)

f Unused drug and diary to be collected during standard of care visit, no other research activities will be performed.

g Insulin, Leptin, Adiponectin, IGF-I and IGF-II

h Age, sex, race, and ethnicity

i If available

j Record concomitant medications that are actively being taken at time of consent till completion of study.

k Subjects receiving Metformin only

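### Patients who cannot tolerate metformin leave the study, not just the drug, which can deplete one arm only; later sampling and the analysis set are not stated (separate, minor: normality is not the worst case for rank-sum power)

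*Protocol*

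**What the plan says.** Two rules in the protocol's Trial Design take patients off. Section F, Treatment modifications: "If a patient cannot tolerate the study medication and misses two or more doses in a row, they will be withdrawn from the study". Section G, Subject removal: "Any patient who develops a grade 3 or higher gastrointestinal toxicity while on study will be discontinued". The first removes the patient from the study. The second does not say whether she leaves the drug or the study.

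Only one arm has study medication. Section A: "Group 1 will receive treatment with metformin, while Group 2 will receive no treatment".

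Sampling is described in general terms. The Protocol Summary says "All subjects will have blood samples collected on Day 1 (prior to start of metformin for subjects randomized to metformin) and prior to surgery". Section B places the second draw "after completion of the therapy at the time of surgery". Section C takes surgical tissue "from the tissue remaining after normal gross and histological assessments". None of these mentions a patient who has been withdrawn.

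Statistical Considerations, in the protocol and again in the SAP, specify rank-sum tests between arms at a two-sided 10% level. They name no analysis set, no rule for missing samples and no allowance for dropout. Sample Size and Power gives 91.6% power for a 1.0 SD difference with 20 per arm, against a criterion of more than 90%, and describes normal distributions as the worst case for that calculation.

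**The concern.** The withdrawal rule acts after randomisation, is triggered by the treatment, and has no counterpart among controls. If withdrawal ends sampling, the patients left in the metformin arm are those who tolerated the drug, while the control arm keeps everyone. Randomisation then no longer protects the comparison on the tissue markers, which are primary endpoints. The primary test uses tissue obtained at surgery, and the Study Calendar has pre-study tissue collected only if available, so the plan offers no baseline adjustment for selective loss.

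Even if samples are collected, the plan does not say whether these patients are analysed. Two analysts following it could report different primary results. With 20 per arm, each patient is 5% of her arm.

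The power statement is affected too. It takes all 40 patients as analysed and all 20 on metformin as showing the full effect, and it treats the normal case as a floor on power.

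**Working it through.** **Inputs from the documents:** 20 per arm; two-sided alpha 0.10; difference 1.0 SD; criterion more than 90% power; stated power 91.6%. **Assumptions** (the documents give no figure): number of metformin patients lost or off drug, k = 1 to 4 of 20; correlation rho between intolerance and a marker, 0, 0.3 or 0.5; effect in a patient who stops drug, zero or half.

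**1. The plan's own figure.** For normal data the rank-sum test has efficiency 3/π = 0.955 relative to the t-test, so 20 per arm acts like 20 × 0.955 = 19.1. Noncentral-t power with 19 per arm uses df = 36 and noncentrality 1.0 × √(19 × 19/38) = 3.08, and gives 91.60%. With 19.1 per arm it is 91.7%. Direct simulation of the rank-sum test gives 91.3% (exact) and 91.7% (asymptotic). The stated 91.6% reproduces.

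**2. Bias if withdrawn patients are not sampled, with no drug effect.** Drop the k least tolerant of 20. The mean marker shift in those remaining is

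shift = rho × (sum of the k largest expected normal order statistics of 20) / (20 − k).

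The four largest are 1.867, 1.408, 1.131 and 0.921.

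- k = 1: 1.867/19 = 0.098; × 0.3 = 0.03 SD, × 0.5 = 0.05 SD
- k = 2: 3.275/18 = 0.182; × 0.3 = 0.05 SD, × 0.5 = 0.09 SD
- k = 4: 5.327/16 = 0.333; × 0.3 = 0.10 SD, × 0.5 = 0.17 SD

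Simulated rank-sum type I error (nominal 10%; 200,000 runs; the ranges span exact and asymptotic p-values):

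| k lost | rho 0.3 | rho 0.5 |
|---|---|---|
| 1 | 9.7–10.3% | 10.2–10.8% |
| 2 | 10.5% | 11.5% |
| 4 | 11.1–11.8% | 13.7–14.5% |

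With rho = 0 there is no shift and the error is 9.5 to 10.1%. The sign of rho is unknown, so the direction of the bias is too.

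**3. Power under each analysis choice** (normal data, 1.0 SD effect in patients who stay on drug):

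| k of 20 | Completers only, 20 − k v 20 | As randomised, zero effect in k | As randomised, half effect in k |
|---|---|---|---|
| 1 | 90.5–91.1% | 88.5–89.1% | 89.9–90.4% |
| 2 | 90.1% | 85.0–85.7% | 88.5–89.0% |
| 3 | 89.0–89.6% | 80.8–81.7% | 86.8–87.5% |
| 4 | 87.9–88.5% | 75.8–76.7% | 85.1–85.8% |

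One zero-effect patient is enough to take the as-randomised comparison below 90%. Completers fall below it from three.

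**4. Is normality the worst case?** Simulated power at a 1.0 SD shift, 20 per arm: normal 91.3–91.7%, uniform 88.5–89.1%, double-exponential 96.2–96.4%. The lower bound on rank-sum efficiency relative to the t-test, 0.864, gives 89.1% by the noncentral-t method in step 1. Shapes less favourable than the normal exist, and they fall just under the criterion.

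**The case against.** The strongest objection is size. With one or two patients lost, type I error barely leaves 10%. It approaches 15% only with four lost and a correlation of 0.5, and the documents support neither input. Section F also allows supportive medication, and treatment lasts only 14 to 21 days. This stands: the marker bias is small. It does not settle who is analysed, which is the gap.

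Three stronger readings are tempting and are not supported.

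- A reader might infer that the Study Calendar bars sampling of withdrawn patients, because footnote f says "Unused drug and diary to be collected during standard of care visit, no other research activities will be performed". That footnote belongs to the post-operative / early-termination column and applies equally to completers. Blood and tissue sit in the surgery column, which it does not restrict.
- A reader might infer that intolerance will be under-reported. Risks and Benefits puts diarrhoea at 50%, or 10 of 20; discarding 2 or 4 withdrawn cases would give 8/18 = 44% or 6/16 = 38%. But nothing in the documents discards recorded adverse events, and the plain reading of the tolerability analysis includes them. These figures are hypothetical.
- A reader might infer that Section G is also confined to one arm. It is worded for any patient; only the Section F rule is confined to metformin.

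It can also be said that a treated-patient analysis is legitimate in a proof-of-concept study. It is, if prespecified. It still gives up the protection of randomisation, so it fits better as the secondary analysis.

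On power, no passage suggests that the markers are uniform, and some shapes gain power. That keeps the wording point minor.

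**Conclusion.** The point holds. As written, withdrawal for intolerance can remove patients only from the metformin arm, and the plan leaves open whether they are sampled and whether they are analysed. It should be fixed. The reason is an undefined primary comparison that is cheap to define, not a demonstrated large bias. If such patients are lost, the marker bias is 0.03 to 0.09 SD with 1 or 2 lost (type I error about 10 to 11.5%) and 0.10 to 0.17 SD with 4 lost (about 11 to 14.5%). All of this is conditional on an assumed number lost and a correlation of 0.3 to 0.5. At zero correlation only power is affected.

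The worst-case wording is a separate, minor error. The 91.6% is correct for normal data with all 40 patients analysed and the full effect throughout the metformin arm. The claim of more than 90% is not established beyond that case.

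**What to change.** 1. Leave the drug-stopping triggers as they are. Reconcile Sections B, F and G of Trial Design so that stopping study drug does not by itself end the planned pre-surgery blood draw and leftover-tissue collection, unless consent is withdrawn. Say in Section G what the patient is discontinued from.
2. In Statistical Considerations of both documents, make the primary comparison all randomised patients with samples, in the assigned arm, with completers as secondary.
3. Confirm in one sentence that adverse events recorded up to withdrawal count in the tolerability analysis.
4. In Sample Size and Power of both documents, say that 91.6% assumes the full effect in all 20 metformin patients, and give the as-randomised figures for drug-stoppers.
5. In the same place, replace the worst-case wording with a plain statement that normal distributions are assumed, and limit the claim of more than 90% to that case.

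**Cost.** No extra patients are needed. On surgery the protocol says "Except in rare circumstances, all these women will be scheduled for hysterectomy"; the tissue is left over from routine pathology, and the second draw is already planned. It does mean some continued research sampling in patients off drug, including lipids and HbA1c, which the Study Calendar marks as above standard of care. The statistical price is dilution: with 1, 2, 3 or 4 of 20 showing no effect, power is about 89%, 85–86%, 81–82% or 76–77%. For a pilot, reporting that lower figure without enlarging the trial is acceptable.

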#### **G. Subject removal**

Any patient who develops a grade 3 or higher gastrointestinal toxicity while on study will be discontinued. Subjects that withdraw from the study or that are withdrawn from the study due to unacceptable toxicity will return all unused study drug at their next scheduled clinic appointment.

#### **H. Study Drug**

Metformin (Fortamet®; Glucophage®; Glucophage® XR; Glumetza®; Riomet®)

Description:

Metformin is an oral antihyperglycemic drug used in the management of type 2 diabetes.

Molecular formula: C4H11N5 • HCl

Molecular weight: 165.62

Adverse Events:

>10%: Gastrointestinal: Diarrhea. Neuromuscular & skeletal: Weakness.

1% to 10%: Cardiovascular: Chest discomfort, flushing, palpitation. Central nervous system: Headache, chills, dizziness, lightheadedness.

Dermatologic: Rash. Endocrine & metabolic: Hypoglycemia.

Gastrointestinal: Indigestion, abdominal discomfort, abdominal distention, abnormal stools, constipation, dyspepsia/ heartburn, taste disorder.

Neuromuscular & skeletal: Myalgia. Respiratory: Dyspnea, upper

respiratory tract infection. Miscellaneous: Diaphoresis increased, vitamin B12 levels decreased, flu-like syndrome, nail disorder

<1%: Megaloblastic anemia

Postmarketing and/or case reports: Lactic acidosis, leukocytoclastic vasculitis, pneumonitis.

#### Pregnancy and Lactation:

Metformin is classified as FDA pregnancy risk category B. Adverse events have not been observed in animal studies; therefore, metformin is classified as pregnancy category B. Metformin has been found to cross the placenta in concentrations which may be comparable to those found in the maternal plasma. Females of childbearing potential should be instructed to avoid becoming pregnant during the study. It is known that low amounts of metformin are excreted into breast milk.

Administration (Dosing): See Trial Design section above

#### Storage and Stability:

Tablets: Store between 20 - 25°C; excursion permitted to 15 - 30°C.

## Study Population

Subjects are eligible for the study if the following inclusion and exclusion criteria are met:

### A. Inclusion Criteria

1. Histological confirmed diagnosis of grade I or II adenocarcinoma of the endometrium
2. Must be obese as defined by a BMI greater than or equal to 30 kg/m^2
3. Candidate for surgical removal of their uterus as part of their endometrial cancer treatment
4. Subjects must have signed informed consent
5. Age 42 - 75 years of age
6. ECOG Performance status of 0 – 2
7. History of adequate renal, liver, and bone marrow function:
  - a. Hb: (adequate for surgical intervention, with transfusion if necessary)
  - b. WBC: (normal range)
  - c. Platelets: (180K/cmm)
  - d. LFTs: Normal bilirubin (<2.0mg/dL), AST/ALT (2xULN)
  - e. Renal function: creatinine less than 1.4
8. Female subjects must either not be of child-bearing potential or must have a negative urine pregnancy test within 7 days of randomization to metformin. Subjects are considered not of child-bearing potential if they are surgically sterile or they are postmenopausal for greater than 12 months.

## **B. Exclusion Criteria**

1. Poorly differentiated cancer or any of the high-risk subtypes of endometrial cancer including serous, clear cell, or carcinosarcoma
2. History of diabetes mellitus Type 1 or Type 2.
3. Receiving metformin prior to enrollment
4. Known hypersensitivity to metformin.
5. Unable to swallow and retain oral medication.
6. Pregnant or lactating.
7. Previous or concurrent malignancies, except non-melanoma skin cancers, unless curatively treated and with no evidence of recurrence for > 5 years
8. If the physician feels that the candidate is not suitable for the study, he/she will be excluded.
9. Currently taking biguanides, sulfonylurea drugs, thiazolidenediones, insulin, or mTOR or DPP-4 inhibitors or having taken any of these medications during the 12 weeks prior to study participation.
  
10. Clinical symptoms of gastrointestinal obstruction or bleeding and consideration for immediate surgery or immediate neoadjuvant chemoradiation.
11. History of lactic or other metabolic acidosis.
12. Uncontrolled infectious disease.
13. History of positivity for human immunodeficiency virus (HIV).
14. History of congestive heart failure requiring pharmacologic treatment.
15. History of excessive alcohol abuse, defined by a habitual intake of more than three drinks daily.
16. Mal-absorption syndrome, disease affecting gastrointestinal function, or previous resection of the stomach or small bowel.
17. Current use of medications for weight loss.

